7.2.2.4 Protocol specifications

Some events should not be considered as SAE.

In this protocol, the following events **are not to be considered as SAE:**

- All hospitalizations for medical or surgical treatment scheduled before study start.
- All hospitalizations for routine treatment or monitoring of the studied pathology not associated with a deterioration of the patient's condition.
- Admission for social or administrative reasons.
- Outpatient hospitalization,

- Progressions related to the disease under study.
- Deaths related to disease under study progression.

7.3 Sponsor obligations

7.3.1 SAE Analysis

The sponsor should assess:

- Causality of serious adverse events (all adverse events, for which there is a reasonable possibility that there is a causal relationship between the study drug/procedure and the event, should be qualified by the investigator or sponsor as reasonably suspected adverse events. If the assessment by the sponsor and the investigator are different, both opinions are mentioned in the report to the competent authority if required).
- The sponsor should qualify the SAE in suspected expected serious adverse reaction or in Suspected Unexpected Serious Adverse Reaction (SUSAR). The evaluation of expectedness is based on knowledge of the adverse reaction and the study drug/procedures. The sponsor should maintain detailed records of all serious adverse events reported by the investigators. These records will be forwarded to the National Health Authority (ANSM), upon request.

7.3.2 Relationship Scoring

In accordance with the ICH Recommendations on the Management of Adverse Events in Clinical Trials, ICH E2B(R3), version of May 12, 2005, a relationship assessment should be performed for any reported SAE.

EVCTM (EudraVigilance Clinical Trial Module) criteria should be used: reasonable possibility / no reasonable possibility.

7.3.3 Notification of SUSARs to competent authorities

The sponsor should report all Suspected Unexpected Serious Adverse Reaction (SUSAR) to the EMA (European Medicines Agency - Eudravigilance database), the French Health Authorities (ANSM), and the principal investigators.

In accordance with article R1123-53 of the Public Health Code, Suspected Unexpected Serious Adverse Reaction (SUSAR) should be reported to the competent authorities from the day the sponsor becomes aware of them:

- Without delay for death and life-threatening SUSAR,
- Until 15 calendar days for all other SUSAR.

Relevant additional Follow-up information regarding SUSARs should be reported to the EMA, ANSM and the investigators within eight days of the initial report.

7.3.4 Notification of New Safety Issue

The sponsor is responsible for alerting the principal investigator in case of identification of a New Safety Issue and should propose urgent measures to be implemented.

The sponsor is responsible for reporting to the competent authorities, **without delay**, any New Safety Issue and the proposed measures.

Relevant follow-up information regarding any New Safety Issue should be reported to the competent authorities within a new delay of 8 days.

7.3.5 Reporting of DSURs (Development Safety Update Report)

On the anniversary date of the Health Authorities trial authorization, the sponsor should report an Annual Safety Report (ASR) consisting of three parts:

- Part 1: Analysis of patient safety.
- Part 2: the list of all suspected serious adverse events (including unexpected serious adverse events) that occurred in the trial in France (and abroad, including in third countries) during the period covered by the report.
- Part 3: summary tables of all serious adverse events and serious adverse reactions that have occurred in the trial since the study start.

This report is sent to the competent authorities (ANSM), Ethics Committee (CPP) and principal investigators within 60 days of the anniversary date of the trial authorization.

7.3.6 Reporting of other safety data

The sponsor should report any safety data or new safety event to the competent authorities (ANSM and CPP) **as soon as possible and no later than 15 calendar days** from the first time the sponsor became aware of the minimum information for immediate reporting.

Relevant additional information must be transmitted within 8 days and 15 days new delay.

7.3.7 In utero exposure

If a patient becomes pregnant during the study, the pregnancy must be reported to the sponsor within a time frame defined by the sponsor.

The investigator informs the sponsor using a standard "Initial Pregnancy Data Collection" sheet. This form should include the expected date of delivery, the contact details of the obstetrician and of the planned maternity hospital if the pregnancy is ongoing.

The investigator should follow the patient until completion of the pregnancy and should notify the sponsor of the outcome using a standard pregnancy outcome form.

If the outcome of the pregnancy meets the criteria for immediate classification as an SAE (i.e., postpartum complication, spontaneous abortion, stillbirth, neonatal death, or congenital anomaly), the investigator should follow the procedures for reporting an SAE.

8. STATISTICAL METHODS AND SAMPLE SIZE DETERMINATION

The analysis will cover 12 patients.

8.1 Brief reminder of study objectives

8.1.1 Primary objective

To assess the concordance for tumor lesion detection using ^{89}Zr -TLX250 PET/CT versus a conventional ^{18}FDG PET/CT scan where comparison will be made on a per lesion analysis basis.

8.1.2 Endpoints of primary objective

Concordance study of metastatic uptake seen in ^{18}FDG PET/CT scan and ^{89}Zr -TLX250 PET/CT scan per "lesion" by comparing for each lesion the CT scan, ^{18}FDG PET scan and ^{89}Zr -TLX250 PET/CT scan by assessing a ratio "Number of positive or negative ^{89}Zr -TLX250 lesions / Number of positive or negative FDG lesions" and "Number of positive or negative ^{89}Zr -TLX250 lesions / Number of CT scan lesions".

8.1.3 Secondary objectives

4. To determine the percent of total tumor burden (whole body) detected on ^{89}Zr -TLX250 PET/CT scan compared to that defined on ^{18}FDG PET/CT used as the reference.
5. To assess the correlation between the normalized uptake values (SUV) of ^{89}Zr -TLX250 and CAIX histological expression if a biopsy is done.
6. To confirm the perfect safety and tolerability of ^{89}Zr -TLX250 and assess the generation of human anti-chimeric antibodies in response to the girentuximab.

8.1.4 Endpoints of secondary objectives

4. Percent of positive CA IX metastatic tumor burden compared to total metastatic tumor burden by ^{18}FDG (ratio "Number of positive ^{89}Zr -TLX250 lesions / Number of positive FDG lesions")
5. If a metastasis biopsy is conducted, assessment of the correlation between the normalized uptake values (SUV) of ^{89}Zr -TLX250 positive lesions and CAIX histological expression will be done by comparing the ^{89}Zr -TLX250 semi-quantitative data with the immunohistochemical results (IHC) of biopsied metastases.
6. The safety and tolerability of ^{89}Zr -TLX250 will be evaluated by measuring and monitoring vital signs within 2 hours after injection of the radiopharmaceutical. The patient will be informed that in the event of abnormal physical signs, occurring within 24 hours after ^{89}Zr -TLX250 administration, he must report them to the investigator for registration. The reporting period of AEs (related to ^{89}Zr -TLX250) and SAEs cover a period of 30 days after ^{89}Zr -TLX250 administration.

- ⇒ The NCI Common Toxicity Criteria, version 5.0 reference will be used.
- ⇒ HACA (Human anti-chimeric antibody) will be assessed.

8.1.5 Exploratory objectives

For 5-6 patients, assessment of the absorbed doses received by organ and in whole body after ⁸⁹Zr-TLX250 administration for imaging purpose in metastatic TNBC patients.

For these patients, blood samples will be drawn at D0 (before ⁸⁹Zr-TLX250 administration), D1, D3, D5 and D7.

Each sample will be analyzed for serum ⁸⁹Zr radioactivity levels in the local nuclear medicine department.

8.1.6 Endpoints of Exploratory objectives

For 5-6 patients, quantitative biodistribution of ⁸⁹Zr-TLX250 evaluated from sequential whole body PET-CT imaging D0, D1, D3, D5 and D7 and pharmacokinetic data (blood samples taken before injection and at the same time of imaging).

8.2 Determination of sample size

As this study is a proof-of-concept, exploratory and descriptive pilot study, the sample size determination is not based on statistical considerations, it is planned to enrol 12 evaluable patients.

8.3 Selection of patients to be included in the statistical analysis

All included patients will be analysed.

8.4 Study feasibility

The estimated duration of study recruitment is approximately 12 months.

8.5 Interim analyses

Not applicable.

8.6 Statistical criteria for study termination

Not applicable.

8.7 Handling of missing, unused or invalid data

Special care will be taken to minimize any missing data for the 12 patients enrolled.

8.8 Description of analysis sets

8.8.1 For Safety Analysis Set:

The frequency and severity of the clinical and biological effects collected over a period of 15 days then at 3 months following the completion of the ^{89}Zr -TLX250 PET/CT will be described by means of frequency of their respective modalities. HACA test at the visit at 3 months post ^{89}Zr -TLX250 PET/CT.

8.8.2 For the determination of ^{89}Zr -TLX250 PET-CT preliminary analysis of diagnostic performance:

From the reference ("gold standard") determined for each patient from all imaging and histology screening data and/or 3-months imaging follow-up (RECIST 1.1 criteria, or PERSIST criteria). The reporting qualitative and semi-quantitative parameters of the lesions will be established at D5 post-injection. The diagnostic performance of ^{89}Zr -TLX250 PET/CT obtained at the post-injection delay considered optimal related, ^{18}FDG PET/CT scan and CT scan compared to gold standard will be described by the sensitivity, specificity, positive and negative predictive values (with their 95% CI) and compared by means of Mc Nemar test. Concordance between techniques will be described by means of Kappa.

Total number of lesions (gold-standard) will be the number of lesions identified by at least one modality.

Lesion detection rates per imaging modality and combined imaging modalities (CT combined with PET) will be estimated with their 95% CI and compared by Wald test, overall and according to organ sites.

Agreement in detecting lesions between modalities will be assessed using kappa's (95%CI).

Furthermore, we will compare the median number of affected organ sites across patients assessed by ^{18}FDG -PET/CT or ^{89}Zr -girentuximab-PET/CT using Wilcoxon signed rank tests.

The physiological biodistribution of ^{89}Zr -girentuximab will be described in normal tissues (lung, liver) using geometric mean SUVmean.

Short Title : **OPALESCENCE**
Ref ICO : ICO-2020-25
N° EudraCT : 2020-003805-71

The overall geometric mean ⁸⁹Zr-girentuximab or ¹⁸FDG SUVmax will be used to quantify uptake in lesions. Link between uptake and lesions location and lesions diameter on CT will be tested.

Correlation between ¹⁸FDG -uptake and ⁸⁹Zr-girentuximab-uptake will be calculated by Rho's coefficient (Spearman test).

8.8.3 For ancillary study set:

The dose received for healthy tissues, the effective dose received for the whole body from sequential whole-body imaging and pharmacokinetic data (at D0, D1, D3 and D7) will be described by means of mean, standard deviation, median, minimum, maximum and interquartile range.

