2.2.2 Endpoints of secondary objectives

1. Percent of positive CA IX metastatic tumor burden compared to total metastatic tumor burden by ^{18}FDG (ratio "Number of positive ^{89}Zr -TLX250 lesions / Number of positive FDG lesions")
2. If a metastasis biopsy is conducted, assessment of the correlation between the normalized uptake values (SUV) of ^{89}Zr -TLX250 positive lesions and CAIX histological expression will be done by comparing the ^{89}Zr -TLX250 semi-quantitative data with the immunohistochemical results (IHC) of biopsied metastases.
3. The safety and tolerability of ^{89}Zr -TLX250 will be evaluated by measuring and monitoring vital signs within 2 hours after injection of the radiopharmaceutical. The patient will be informed that in the event of abnormal physical signs, occurring within 24 hours after ^{89}Zr -TLX250 administration, he must report them to the investigator for

registration. The reporting period of AEs (related to ^{89}Zr -TLX250) and SAEs cover a period of 30 days after ^{89}Zr -TLX250 administration.

- ⇒ The NCI Common Toxicity Criteria, version 5.0 reference will be used.
- ⇒ HACA (Human anti-chimeric antibody) will be assessed.

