6.2 Enrolment

Patient Enrolment may occur only after the completion of the screening evaluations and confirmation of subject eligibility.

Enrolment will be centralized and performed via the eCRF.

How to connect to the eCRF:

- Go to website: <https://www.cancero-go-online.org/CSOnline/>
- Study code: **CRGA0065**
- Study Sponsor number : ICO-2020-25
- Username and password: Nominative and personal, they will be given to each participant after investigation site participation setup visit opening of the site.

If the software is unavailable, the enrolment registration request will be centralized at the sponsor ICO “Service Promotion de la Recherche Clinique”. A registration Form is provided for this purpose.

It will be sent by e-mail to the sponsor (between 9am and 5pm). An enrolment number will be assigned to the patient and e-mailed to the site.

Sponsor Contact Information : DRC de l'ICO / Cellule de Promotion

Tél. : [name]

Chef de Projet : [name]

E-mail : [contact]

After the enrolment procedure is completed, the investigator will receive by email a confirmation of the patient enrolment, the centre identification number, the patient identification number.

After the enrolment, each patient will receive a “**patient card**” (Appendix 6) specifying the procedure received in the trial. The patient may present this card to any health professional encountered during the trial.

6.3 ⁸⁹Zr-TLX250 PET/CT Imaging

6.3.1 ⁸⁹Zr-TLX250 administration

The following examinations and procedures will be performed on Day 0 before ⁸⁹Zr-TLX250 administration:

- Physical exam.
- Pre-dose Vital signs.
- Pregnancy test from urine (for female patients of childbearing potential) within 72 hours before ⁸⁹Zr-TLX250 administration.

- Baseline findings.
- Concomitant medication.

Administration of ⁸⁹Zr-TLX250 will be slowly conducted over a minimum of 3 minutes via the IV route (see Section 5.2.1). The intravenous line should be flushed slowly with normal saline and the end of administration time recorded.

The dose syringe should be assayed for residual radioactivity and the net activity administered to the patient recorded.

Vital signs will be assessed immediately after the slow injection of ⁸⁹Zr-TLX250 dose, 30 minutes, 1 hour and 2 hours after ⁸⁹Zr-TLX250 administration.

Adverse event monitoring will be assessed within 2 hours post administration.

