If adverse events occur within 30 days post administration, the patient must inform the investigator. These adverse events will be reported in the e-CRF.

6.3.2 ⁸⁹Zr-TLX250 Imaging

On D5 ± 2 days post administration of ⁸⁹Zr-TLX250, a whole body PET/CT imaging will be performed from skull to mid-thigh using 6-8 bed positions with 10 minute acquisition time per bed position.

Laboratory assessments will be performed: Blood count, creatinine clearance, glucose, bilirubin, ALAT, ASAT, Alkaline Phosphatases, and Gamma GT.

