7.2 Investigator obligations

7.2.1 Adverse Events reporting

Adverse Events will be recorded in the corresponding section of the e-CRF.

For this study, all adverse events related to ⁸⁹Zr- Girentuximab PET/CT should be recorded in the e-CRF **from the date of administration of ⁸⁹Zr- Girentuximab until 30 days after administration.**

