7.2.2.3 Notification to the sponsor

The investigator must **immediately (without delay)** and **no later than 24 hours** following knowledge of the event, notify the sponsor pharmacovigilance unit of **any SAE or any new issue** defined in section 7.1.2:

- **from informed consent signature up to $^{89}\text{Zr-TLX250}$ administration:** only SAE related to the study procedures must be reported to the sponsor.
- **from $^{89}\text{Zr-TLX250}$ administration up to 30 days post- $^{89}\text{Zr-TLX250}$ administration:** all SAEs, whether or not related to the study drug/procedure, must be reported to the sponsor.

All delayed Serious Adverse Events (occurring after this period) considered reasonably related to $^{89}\text{Zr-TLX250}$ must be reported without time limit.

Except those that are identified in the protocol as not requiring immediate reporting.

This initial SAE notification shall be followed promptly by a detailed written follow-up report(s) until event resolution.

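### The safety analysis in 8.8.1 summarises 15 days after the PET/CT, but the safety endpoint runs 30 days from administration, and no reading of the 15 days reaches day 30

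*Combined protocol and SAP*

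**What the plan says.** Section 8.8.1 is headed as the safety analysis set. It says that clinical and biological effects "collected over a period of 15 days then at 3 months following the completion of the" tracer PET/CT will be described by frequency and severity, and it adds the HACA test at 3 months. It does not say which patients form the set.

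The endpoint is defined differently:

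- **8.1.4:** safety and tolerability "will be evaluated by measuring and monitoring vital signs within 2 hours after injection of the radiopharmaceutical", with patient reports of abnormal signs over the first 24 hours. The sentence that opens "The reporting period of AEs (related to" the tracer sets 30 days after administration.
- **2.2.2:** the same rule; related adverse events "and SAEs cover a period of 30 days after" administration.
- **6.3.1:** "If adverse events occur within 30 days post administration, the patient must inform the investigator".
- **7.2.1:** related adverse events are recorded in the eCRF from the day of administration "until 30 days after administration".
- **7.2.2.3:** over the same 30 days, "all SAEs, whether or not related to the study drug/procedure, must be reported to the sponsor".

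The imaging scan is at D5 ± 2 (schedule, footnote f; 6.3.2). The schedule places AE/SAE review at D0, D1, D3, D5, D7, D30 and D90.

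**The concern.** The analysis period and the endpoint period disagree in length (15 against 30 days) and in starting point (completion of the PET/CT against administration). No other section supports 15 days: the ± 15 days in 6.5 is a tolerance on the 3-month visit, and no visit falls at D15 or at D18 to D22, which is 15 days after a D3 to D7 scan. The 3-month part of the sentence does correspond to the visit in 6.5.

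The meaning of PET/CT adds a second ambiguity. If it is the scan alone, the summary starts 3 to 7 days after injection. It then leaves out the 2-hour vital signs and 24-hour reports named in 8.1.4, and the period in which 1.4.3 says allergic-type reactions are possible. If it is the whole procedure, Day 0 is kept. The second reading has support: section 6.3 carries the PET/CT imaging title, yet its first subsection covers administration and begins "The following examinations and procedures will be performed on Day 0 before" the injection.

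The population is unclear as well. Under 4.5, a patient injected but never scanned is a replaced drop-out. Under 8.3 all included patients are analysed, while the opening of section 8 says the analysis covers 12. Such a patient has no completed PET/CT from which to count.

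What is at stake is the reported safety table. An event within the 30 days can only be missed by a shorter window, never added, and the stated objective (8.1.3) is to confirm perfect safety and tolerability.

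**Working it through.** This is a day count; no test or sample-size figure is involved.

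**Inputs.** Endpoint period: day 0 to day 30 after administration (8.1.4, 2.2.2). Analysis period: 15 days (8.8.1). Scan day *s*: 3, 5 or 7 (D5 ± 2). The last ancillary scan is on D7, so it adds no later starting point.

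**Three readings of the 15 days**

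- A, from the scan: [*s*, *s* + 15]. Covered = 15. Lost before = *s*. Lost after = 30 − (*s* + 15).
- B, from injection: [0, 15]. Covered = 15. Lost after = 30 − 15 = 15.
- C, from injection to 15 days after the scan: [0, *s* + 15]. Covered = *s* + 15. Lost after = 30 − (*s* + 15).

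| Reading | Scan day | Period | Covered of 30 | Lost before | Lost after |
|---|---|---|---|---|---|
| A | D3 | D3–D18 | 15 (50%) | 3 | 12 |
| A | D5 | D5–D20 | 15 (50%) | 5 | 10 |
| A | D7 | D7–D22 | 15 (50%) | 7 | 8 |
| B | any | D0–D15 | 15 (50%) | 0 | 15 |
| C | D3 | D0–D18 | 18 (60%) | 0 | 12 |
| C | D5 | D0–D20 | 20 (67%) | 0 | 10 |
| C | D7 | D0–D22 | 22 (73%) | 0 | 8 |

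**Results.** Total days lost range from 8 (reading C, D7 scan) to 15 (readings A and B). The latest possible end is 7 + 15 = D22, so D22 to D30 is never covered. With the nominal D5 scan the latest end is D20. For the 15 days to reach D30 the scan would have to be on day 30 − 15 = D15, outside the permitted D3 to D7.

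**The 3-month time point.** Taking 3 months as 90 days, as the heading of 6.5 does, the visit falls between 3 + 75 = D78 and 7 + 105 = D112 after administration. It is a visit date, and 8.8.1 does not say that it collects everything since the end of the 15 days.

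**A related date.** The schedule puts the follow-up visit at D30. Section 6.4 puts it 30 days after the scan, which is *s* + 30 = D33, D35 or D37 after administration.

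**The case against.** The strongest reply is that 8.8.1 has two parts, and the second may fill the gap. AE/SAE review takes place at both the D30 and the 3-month visits. If the 3-month summary counts everything since the 15-day period ended, events from D22 to D30 are reported after all. That is possible, but 8.8.1 does not say so and names no D30 time point, so a statistician could reasonably do otherwise. It also does not recover the days before the scan on reading A.

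Other points reduce the consequence:

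- Serious events appear in the annual safety report tables whatever 8.8.1 says (7.3.5), and all patient files are fully monitored (9.2.2). Those tables cover serious events only, so the exposure is mainly the non-serious events in the trial's own report.
- Post-dose haematology and chemistry are scheduled only at the imaging visit, so no scheduled laboratory value from D22 to D30 can be lost.
- The one expected reaction is mild nausea in under 10% of 69 patients (7.1.3). That is fewer than 0.10 × 12 = 1.2 patients here, with no timing given. The loss can therefore be stated in days but not in events.
- A careful statistician might follow 8.1.4 instead of 8.8.1. That is true, and it confirms that the two passages give different tables.

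On population, 8.3 does name one (all included patients). It does not settle who is in the safety set, because 4.5 replaces drop-outs and section 8 fixes the number analysed at 12.

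**Conclusion.** The concern holds. As written, the 15-day summary in 8.8.1 covers between 15 and 22 of the 30 endpoint days, leaving out 8 to 15, and the last 8 (D22 to D30) are outside it on every reading and every permitted scan day. This assumes only that the scan is within D3 to D7 and that the 3-month summary is not cumulative, which the text leaves open. Whether injection day is also lost depends on what PET/CT means in that sentence.

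The data are collected, there is no safety test, and the study is a descriptive pilot, so no inferential result is at risk. The defect is a prespecified table that does not match its endpoint and can be built in more than one way. It should be corrected before the analysis.

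**What to change.** Rewrite 8.8.1 to:

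1. Define the safety set as all patients who received the injection, including drop-outs who were later replaced, and say how this relates to 8.3 and to the 12 patients in section 8.
2. Summarise AEs and SAEs from the start of administration through 30 days after administration, as in 8.1.4, together with the Day 0 vital signs and the imaging-visit laboratory values (6.3.2).
3. List separately the 3-month review findings (6.5), later related SAEs and HACA. Procedure-related SAEs between consent and administration (7.2.2.3) can be listed there too, since they precede the endpoint period.

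The cost is a wording change in 8.8.1, with a cross-reference to 8.3 if wanted. No new data are collected.

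Two neighbouring inconsistencies should be reconciled by the sponsor at the same time, although the main fix does not depend on them. The follow-up visit is at D30 in the schedule but 30 days after the scan in 6.4. Adverse events within 30 days are reported without regard to relatedness in 6.3.1, but only if related in 2.2.2, 8.1.4 and 7.2.1. Both are text changes; the second touches either 6.3.1 or the other three sections.

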5.2.3 Imaging Analysis

5.2.3.1 ⁸⁹Zr-TLX250 Tumor Targeting

⁸⁹Zr-TLX250 tumor uptake will qualitatively be assessed, considering whether or not ⁸⁹Zr-TLX250 binding the target lesions determined on FDG PET-CT as metastatic lesions.

The interpretation of the ⁸⁹Zr-TLX250 PET/CT images as positive or negative for metastatic TNBC will be made on the basis of visual examination only.

The ⁸⁹Zr-TLX250 PET/CT images will be evaluated for evidence of radioactive uptake in the metastatic TNBC lesions. The local and central reviewers will designate the lesions as having a status of positive or negative.

The ⁸⁹Zr-girentuximab PET/CTs will be assessed in a central reviewing system to ensure true lesion detection and reproducible inter-observer agreement. All ⁸⁹Zr-girentuximab PET/CTs would be assessed by two expert nuclear physicians independently.

The first evaluation will be done by the nuclear physician, in charge of the patient during the ⁸⁹Zr-girentuximab PET/CT exam.

The second evaluation will be done by a second nuclear physician who should be blinded for evaluation of the first nuclear physician. However, for patient safety reasons, the nuclear physician should be allowed to communicate findings that required (local) interventions (e.g. brain metastases).

The two reports would be harmonized to one final report by the first reviewer. In case of different findings, a third nuclear physician should evaluate the ⁸⁹Zr-girentuximab PET/CT exam to reach a consensus.

A tumor lesion will be defined visually positive based on anatomical substrate on low-dose CT in combination with ¹⁸FDG and/or ⁸⁹Zr-girentuximab-uptake. Quantification of positive lesions as defined by evaluation reports for ¹⁸FDG and ⁸⁹Zr-girentuximab PET/CT will be performed by drawing regions-of-interest using dosisoft (PLANET Edition 3 – PLANET Onco Dose, Version 3.1.1.50 – 2021-01-03).

The maximum and mean standardized uptake values (SUV) will be calculated. SUVmax will be used for tumor tracer-uptake; SUVmean for measuring uptake in healthy organs and blood pool.

The lesion will be classified as PET-positive if:

- Radioactivity in the lesion is clearly visible (as described above), **AND**
- With a same location as FDG positive lesions described previously.

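### Section 8.8.2 plans kappa for per-lesion agreement, but on the only lesion list it defines kappa cannot exceed 0 without CT-only lesions and otherwise depends on their number; McNemar does not fit PPV and NPV

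*Combined protocol and SAP*

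**What the plan says.** The primary objective (sections 2.1.1 and 8.1.1) is concordance between 89Zr-TLX250 PET/CT and FDG PET/CT, judged lesion by lesion. Its endpoint (2.1.2 and 8.1.2) is a pair of lesion-count ratios, 89Zr over FDG and 89Zr over CT. Both positive and negative lesions are counted for the two tracers.

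Section 8.8.2 adds the following.

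- **Agreement:** "Concordance between techniques will be described by means of Kappa". Kappa is named a second time, with a 95% confidence interval, for how far the modalities agree on lesions.
- **Lesion list:** "Total number of lesions (gold-standard) will be the number of lesions identified by at least one modality". There is no rule for listing sites that are negative on all scans.
- **Accuracy:** a composite reference is "determined for each patient from all imaging and histology screening data and/or 3-months imaging follow-up". Against it, the performance of the scans "will be described by the sensitivity, specificity, positive and negative predictive values (with their 95% CI) and compared by means of Mc Nemar test".

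Section 5.2.3.1 describes 89Zr reading in sentences that do not fit together. Uptake is judged by whether the tracer is "binding the target lesions determined on FDG PET-CT as metastatic lesions". Then: "A tumor lesion will be defined visually positive based on anatomical substrate on low-dose CT in combination with ¹⁸FDG and/or ⁸⁹Zr-girentuximab-uptake". Finally, a PET-positive lesion must show visible activity and also meet this condition: "With a same location as FDG positive lesions described previously".

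Section 8.2 describes a descriptive pilot of 12 evaluable patients, with a sample size not based on statistical considerations.

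**The concern.** Kappa compares observed agreement with the agreement expected from the margins of a 2x2 table, so it needs units that both scans could call negative. A list made of lesions that some scan detected supplies such units only through a third scan. The FDG-89Zr kappa would then depend partly on how many lesions CT alone shows, which is not what the primary objective asks.

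Kappa is the only planned agreement coefficient that pairs the scans lesion by lesion. If it is reported without the CT-only count, a low value could be read as poor agreement between tracers when it reflects the make-up of the list.

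A separate fault concerns McNemar, which is assigned to all four accuracy measures. It compares paired proportions over one common set of units. PPV and NPV do not have that structure.

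**Working it through.** **Inputs.** The documents give no lesion counts, so all counts below are assumptions. For each listed lesion let a = positive on FDG and 89Zr, b = FDG only, c = 89Zr only, d = negative on both. On the list of section 8.8.2, d is the number of CT-only lesions. The plan states no kappa value to reproduce.

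**Formula.** kappa = 2(ad - bc) / [(a+b)(b+d) + (a+c)(c+d)].

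**Step 1: no CT-only lesions (d = 0).** kappa = -2bc / [b(a+b) + c(a+c)], which is never above 0. It is exactly 0 when one of b and c is 0, negative when both exceed 0, and 0/0 when both are 0 (perfect agreement). An exact check of all 68,920 tables with a, b, c from 0 to 40 found a maximum of 0. Example (90, 5, 5, 0): -50/950 = -0.05, with raw agreement of 90%.

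**Step 2: CT-only lesions present, FDG and 89Zr reads held fixed.** Positive agreement is 2a/(2a+b+c) and does not involve d.

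| a, b, c | d | kappa | positive agreement |
|---|---|---|---|
| 90, 10, 0 | 0 | 0.00 | 180/190 = 0.95 |
| 90, 10, 0 | 5 | 900/1,950 = 0.46 | 0.95 |
| 90, 10, 0 | 30 | 5,400/6,700 = 0.81 | 0.95 |
| 25, 75, 0 | 0 | 0.00 | 50/125 = 0.40 |
| 25, 75, 0 | 30 | 1,500/11,250 = 0.13 | 0.40 |
| 25, 75, 0 | 100 | 5,000/20,000 = 0.25 | 0.40 |

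The 25% rows borrow the share of TNBCs that express CAIX (section 1.3). That is a tumour rate, used here only as an assumed lesion rate.

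**Step 3: kappa at a fixed d.** With d = 20, kappa is 0.25, 0.44 and 0.75 when 89Zr sees 50, 70 and 90 of 100 FDG lesions. It tracks agreement once d is fixed, but the plan neither fixes d nor asks for it to be reported.

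**Step 4: CT against FDG.** For this pair the both-negative cell holds only 89Zr-only lesions. If the co-location condition of section 5.2.3.1 is applied literally there are none, so step 1 applies and kappa cannot exceed 0. Example with 80 seen on both, 10 on CT only and 10 on FDG only: -200/1,800 = -0.11, with 80% raw agreement.

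**Step 5: McNemar.** Sensitivities are compared over the same reference-positive units and specificities over the same reference-negative units, so pairing works for both. PPV uses each scan's own positives and NPV each scan's own negatives. Suppose 80 of 100 flagged lesions are confirmed, FDG is positive in 87 (72 confirmed) and 89Zr in 61 (56 confirmed). The PPVs are 72/87 = 82.8% and 56/61 = 91.8%, with no common set of pairs.

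The test can also mislead. Take 100 diseased and 100 non-diseased units, where test A has 80 true and 20 false positives, test B has 40 and 10, and B's positives are all among A's. PPV is 80% for both. Exact McNemar gives p = 2 x 0.5^40 = 1.8e-12 in the diseased units and p = 2 x 0.5^10 = 0.002 in the non-diseased units.

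**The case against.** The strongest reply is that CT-only lesions will probably be listed. The primary endpoint counts FDG-negative as well as FDG-positive lesions and counts CT lesions separately, and inclusion criterion 4 admits disease documented by conventional imaging. If co-location rules out 89Zr-only lesions, any FDG-negative lesion on the list must be CT-only, so d is above 0. A CT lesion negative on both tracers is a genuine agreement, and the remaining problem is kappa's familiar dependence on prevalence. This stands. A reader might infer that kappa is bound to be 0 or negative, and the documents do not support that.

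Two routes to that inference fail.

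- The and/or sentence in section 5.2.3.1 says when a lesion is positive, not which lesions are listed. The same section lets readers call a lesion negative, so the sentence does not exclude CT-only lesions.
- Lesions determined on FDG PET-CT need not all be FDG-avid, because the screening examination includes contrast CT. FDG positivity for every listed unit does not follow.

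It is also fair that section 8.8.2 never says kappa is computed on the list of detected lesions. That sentence most directly serves the detection rates. But no other list is defined, and the composite reference brings no rule for listing negative sites.

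Finally, a reader might infer that the same reads could generally pass for no agreement or for strong agreement. The range from 0 to above 0.8 needs the assumed 90% detection. At an assumed 25%, kappa stays at or below 0.25 for up to 100 CT-only lesions.

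**Conclusion.** The point holds as a defect in a stated analysis. On the only lesion list that section 8.8.2 defines, FDG-89Zr kappa cannot exceed 0 without CT-only lesions. With them, the likelier case, it mixes their number with agreement between the tracers. The algebra does not depend on the assumed counts, but the size of the effect does. Applying kappa to this list is an inference from the absence of any other.

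The CT-FDG result in step 4 depends on a literal co-location rule. The McNemar point depends on neither the list nor the counts.

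A reader might infer that the primary analysis is invalid. It is not: the lesion-count ratios and the detection rates are untouched, and the study is a descriptive pilot with no decision rule. A reader might also infer from the gold-standard label that accuracy is measured against the list of detected lesions, which would give specificity of 0/0 and PPV of 100%. The natural reading is that the composite governs accuracy, so the label is a smaller matter of wording.

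**What to change.** In section 8.8.2:

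- Report the paired FDG-89Zr lesion 2x2 table, with positive agreement 2a/(2a+b+c) as the per-lesion concordance measure.
- Show kappa, if kept, only beside these, with the CT-only count and the lesion list it uses.
- Use the list of lesions seen by at least one modality only as the denominator for detection rates. Remove its gold-standard label and keep the composite as the reference for accuracy.
- Restrict McNemar to sensitivity and specificity. Report PPV and NPV with confidence intervals only, or compare them by a paired method made for predictive values.

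In section 5.2.3.1, reconcile the positivity sentences, since they decide whether 89Zr-only lesions can occur.

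The cost is SAP wording and some re-tabulation of reads already made, with no new scans or patients. Kappa is no longer a stand-alone result. Under co-location (c = 0), positive agreement equals 2p/(1+p), where p is the 89Zr/FDG ratio already planned in section 8.1.4 (p = 0.90 gives 0.95, p = 0.25 gives 0.40). It then adds nothing beyond that ratio, and the 2x2 table carries the information.
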